## 7.3 Analysis of Primary and Key Secondary Outcomes

### Primary Hypothesis

Hypothesis: Treatment with LEV improves the rate of seizure termination at 24 hours in neonates compared with standard PB treatment.

Analysis Plan: A Fisher's exact test will be used to test the 24 hours seizure termination rate between the two treatment groups. As a secondary analysis, multivariate logistic regression (if there are sufficient number of events), will be performed to study the association between termination rates and treatment. Pre-specified covariates, including seizure etiology (HIE vs Other)

CONFIDENTIALITY STATEMENT: This report from the USC Alzheimer's Therapeutic Research Institute (ATRI) is for the sole use of the intended recipient(s) and contains confidential and privileged information. Any unauthorized review, use, disclosure, copying or distribution is strictly prohibited.

and hypothermia treatment (yes, no), will be included in the multivariable model as observed confounders.

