It should be remembered that this was the response rate to LEV used as a *second* line agent in subjects refractory to PB as a first line agent. As such this response rate of 42% seen in the higher dose cohort compares favorably with efficacy data for phenytoin and Phenobarbital when used as second line agents. Painter et al. found that of 4 of 17 (24%) neonates with seizures refractory to Phenobarbital responded to the phenytoin as the next AED, and 5 of 16 (31%) neonates with seizures refractory to phenytoin responded to Phenobarbital as the next AED ⁶³.

Two recent publications document retrospectively the response of neonatal seizures to IV LEV. Abend et al. reported that 23 neonates treated with LEV at a low mean initial dosage of 16 mg/kg had a >50% seizure reduction in 35% of infants with seizure termination in 7 of 23 (30%) ⁶⁸. No respiratory or cardiovascular effects were detected. Khan et al. reported that 22 neonates received an LEV load of 10-50 mg/kg and 22 (86%) achieved immediate seizure cessation at 1 hour. No serious side effects were evident; one infant became irritable on treatment responding to 50mg of pyridoxine ⁶⁹.

8. RESEARCH DESIGN AND METHODS: (guideline length is 3-6 pages)

Study Design Summary:

[figure not shown]
This study will be a phase II preliminary efficacy, dose escalation and safety study. The study design will be a randomized blinded controlled treatment study. Infants recognized as having neonatal seizures or as being at risk of developing seizures will be recruited and started on continuous video EEG monitoring. The EEG data will then be reviewed continuously for electrographic seizures by study investigators, along with remote continuous EEG monitoring by Corticare technicians. A novel seizure detection algorithm operating in near-real time will be compared to the real-time continuous EEG reading.

Once eligibility and consent are confirmed, patients will be randomly assigned to the LEV or control treatment group in a 60:40 allocation ratio, stratified by site.

Blinding will be maintained by appropriate dilution of LEV and Phenobarbital such that the same volume (ml/kg) loads are given to both treatment groups.

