## 3 Study Design/Summary

### 3.1 Overview

*This section is from the NEOLEV2 Clinical Research Plan (111361 NEOLEV2 Research Plan Clean 20180413.docx).*

This study will be a phase II preliminary efficacy, dose escalation and safety study. The study design will be a randomized blinded controlled treatment study. Infants recognized as having neonatal seizures or as being at risk of developing seizures will be recruited and started on continuous video EEG monitoring. The EEG data will then be reviewed continuously for electrographic seizures by study investigators, along with remote continuous EEG monitoring by Corticare technicians. A novel seizure detection algorithm operating in near-real time will be compared to the real-time continuous EEG reading. Once eligibility and consent are confirmed, patients will be randomly assigned to the LEV or control treatment group in a 60:40 allocation ratio, stratified by site.

Blinding will be maintained by appropriate dilution of LEV and Phenobarbital such that the same volume (ml/kg) loads are given to both treatment groups.

Subjects randomized to receive LEV will, at the onset of electrographically confirmed seizure activity, receive an intravenous loading dose of LEV of 40mg/kg given over 15 minutes. If electrographic seizures are confirmed to persist or recur more than

CONFIDENTIALITY STATEMENT: This report from the USC Alzheimer's Therapeutic Research Institute (ATRI) is for the sole use of the intended recipient(s) and contains confidential and privileged information. Any unauthorized review, use, disclosure, copying or distribution is strictly prohibited.

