### 3.4 Power and Sample Size Determination

Power calculations were based on a 2-sided chi-square test for detecting a difference between two proportions, assuming a Type 1 error of 0.05. With a sample size of 60 LEV subjects and 40 PB subject and assuming a seizure cessation rate of 50% in the control arm, we have 80% power to detect a seizure cessation rate as low as 22% (an absolute difference in seizure outcome rates of 28% or greater) in the LEV group.

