### 6.2 Multiple Comparisons and Multiplicity

Tests of group differences (active LEV compared to the control PB group) for the primary outcome will be conducted at a two-sided alpha level of 0.05. Similarly, other secondary outcomes will also be conducted using a two-sided alpha level of 0.05. No adjustment for multiple comparisons will be used in this study; however, all results will be reported using point estimates with the corresponding 95% confidence intervals.

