### Key Secondary Hypothesis

Hypothesis: Treatment with LEV improves the rate of seizure cessation at 48 hours in neonates compared with standard PB treatment.

Analysis Plan: A similar approach as used for the primary outcome will be utilized to analyze the 48 hours seizure cessation rates.

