## 7.4 Analysis of Remaining Secondary Outcomes

- Hypothesis 1: Treatment with LEV improves the rate of seizure cessation at 1 hour in neonates compared with standard PB treatment.

Analysis Plan: A similar approach as used for the primary outcome will be utilized to analyze the 1-hour seizure cessation rates.

- Hypothesis 2: Length of seizure freedom will be longer in the LEV group than in the PB group.

Analysis Plan: Actual length of seizure freedom will be summarized by mean and standard deviation as well as quartiles. Comparison between randomization groups will be performed using Wilcoxon-rank sum test.

- Hypothesis 3: Additional LEV treatment in neonates who didn't respond to 40mg/kg LEV will be effective (additional seizure terminations).

Analysis Plan: The percentage of neonates whose seizures stop following 60mg/kg LEV, having not responded to 40mg/kg LEV will be calculated with the corresponding 95% confidence interval.

- Hypothesis 4: LEV treatment will result in a lower dose of phenobarbital being needed as compared to the PB treatment alone.

Analysis Plan: Phenobarbital dose will be summarized by mean and standard deviation as well as quartiles. Comparison between randomization groups will be performed using Wilcoxon-rank sum test.

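### Randomisation is stratified by site, but no analysis of the 24-hour, 48-hour or 1-hour outcome is specified to use site: a cheap efficiency gain, not a validity error

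*SAP*

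**What the plan says.** SAP 3.1 states that "patients will be randomly assigned to the LEV or control treatment group in a 60:40 allocation ratio, stratified by site". Section 8 of the protocol, Study Design Summary, has the same rule and puts randomisation at the point of consent: "Once eligibility and consent are confirmed, patients will be randomly assigned".

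For the primary outcome, SAP 7.3 says: "A Fisher's exact test will be used to test the 24 hours seizure termination rate between the two treatment groups". The key secondary outcome follows it: "A similar approach as used for the primary outcome will be utilized to analyze the 48 hours seizure cessation rates". So does the 1-hour outcome in SAP 7.4: "A similar approach as used for the primary outcome will be utilized to analyze the 1-hour seizure cessation rates". None of these mentions site.

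The secondary logistic model in SAP 7.3 has a covariate list that begins "Pre-specified covariates, including seizure etiology (HIE vs Other" and ends with hypothermia. Site is not named. The protocol's analysis plan for Aim 1 let stratification factors into that secondary model only if they were both unbalanced between arms (p < 0.10) and associated with outcome (p < 0.15). SAP 7.3 does not restate that screen.

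SAP 6.2 adds that "all results will be reported using point estimates with the corresponding 95% confidence intervals". On power, SAP 3.4 assumes 60 and 40 infants and a control rate of 50%, and claims "we have 80% power to detect a seizure cessation rate as low as 22" per cent in the LEV arm.

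**The concern.** If termination rates differ between sites, stratified allocation removes some chance variation between the arms. A pooled test does not know this. It carries the between-site variation as noise and becomes more conservative than it needs to be. Planned power is about 80% with no reserve, so a few points matter.

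Site differences are plausible. Protocol section 8 lets each site's investigator set EEG monitoring at 24 to 48 hours after study drug, which could affect how recurrence is detected, especially for the 48-hour outcome. Historical volumes are also uneven: 39, 12 and 6 to 10 infants per year at the three hospitals listed. What is at stake is efficiency, together with an effect estimate that respects the design.

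**Working it through.** **1. The plan's own figure.** Inputs from SAP 3.4: 60 LEV at 22%, 40 PB at 50%, two-sided alpha 0.05.

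- Pooled rate = (60 × 0.22 + 40 × 0.50)/100 = 33.2/100 = 0.332.
- Null SE = √[0.332 × 0.668 × (1/60 + 1/40)] = 0.0961.
- Alternative SE = √[0.22 × 0.78/60 + 0.50 × 0.50/40] = 0.0954.
- Chi-square power = Φ[(0.28 − 1.96 × 0.0961)/0.0954] = Φ(0.96) = 83.1%.
- Exact enumeration over all 61 × 41 outcomes gives 83.4% for the uncorrected chi-square and **79.6% for Fisher's test**, the planned test. The stated 80% therefore fits Fisher.

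**2. Validity of the planned test.** With the same enumeration under equal rates, Fisher's size peaks at 3.95%, at a common rate of 50%. When sites differ and arms are balanced within site, simulated size falls to about 2 to 3.5%. It never exceeds 5%.

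**3. The alternative.** Condition on each site's margins. Under the null, the number terminated on LEV at site k is hypergeometric. The distribution of the total T over sites is the convolution of these, and p = Σ P(T = j) over all j with P(T = j) ≤ P(T = observed). Size is at most 5% by construction, and about 3.6 to 4.3% in simulation.

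**4. Power comparison.** Assumptions not in the documents: 100 treated infants analysed; six sites (the number named in SAP 3.3) of 34, 20, 16, 14, 10 and 6; normal site effects on the logit scale; overall rates held at 22% and 50%. The middle 90% of sites is expit(±1.645 × SD) around a 50% rate.

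*Treated infants not balanced within site.* 300 infants are randomised within site before seizures are confirmed, and a random third are treated. This follows randomisation at consent and the roughly 3:1 monitored-to-treated ratio in protocol section 10. There were 60,000 trials per row; changes are paired and taken before rounding.

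| Logit SD | Middle 90% of sites | Fisher | Exact stratified | Change (points) |
|---|---|---|---|---|
| 0 | 50% | 79.7% | 78.0% | −1.7 |
| 0.5 | 31–69% | 80.1% | 79.9% | −0.3 |
| 0.6 | 27–73% | 80.4% | 80.7% | +0.3 |
| 1.0 | 16–84% | 80.5% | 83.7% | +3.2 |
| 1.5 | 8–92% | 80.5% | 87.3% | +6.9 |

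Break-even, by interpolation between −0.28 and +0.33: 0.5 + 0.1 × 0.28/(0.28 + 0.33) ≈ 0.55.

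*Treated infants balanced 60:40 within site.* Changes at SD 0 / 0.5 / 1.0 / 1.5 are +0.5 / +1.6 / +4.2 / +7.4 points.

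*Other site sizes, unbalanced case, SD 0 / 0.5 / 1.0.* Six equal sites: −1.6 / −0.1 / +3.0. Sites of 50, 20, 12, 8, 6 and 4: −1.8 / −0.1 / +2.4. Five sites of 20: −1.6 / 0.0 / +3.5.

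**5. Other versions of the stratified test.** The uncorrected asymptotic Cochran-Mantel-Haenszel test beat Fisher in every setting tried, by 1.5 to 9.4 points, with simulated size 4.5 to 5.4%. Much of that lead has nothing to do with site: without strata, the uncorrected chi-square already leads Fisher by 83.4 − 79.6 = 3.8 points by escaping discreteness. The continuity-corrected version loses 4.7 points to Fisher at SD 0 and 3.3 at SD 0.5 in the unbalanced case.

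**6. Site in the logistic model.** Expected events are 60 × 0.22 + 40 × 0.50 ≈ 33. Five site indicators plus treatment, etiology and hypothermia make eight parameters, so 33/8 ≈ 4 events each. Conditioning on site leaves three parameters. Dividing 33 by 3 would flatter that choice, because conditioning uses up information and a site where all or no infants terminate contributes nothing.

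**The case against.** The strongest reply is that nothing is broken: the test is valid, it has the power claimed, and the replacement can do worse. That stands as far as it goes. In the unbalanced case the exact version gains only above an SD of about 0.55, and no section reports an outcome by site. It does not remove the point, because the loss is bounded at under 2 points, the possible gain is larger, and no new data are needed.

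Other parts of the reply also stand:

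- **Site sizes.** The protocol plans 4 to 6 treated infants per site per year, or 16 to 24 over four years, which is nearly equal. The uneven base case is an assumption. The sensitivity runs show that it changes little.
- **Analysis set.** SAP 6.1 defines intention to treat as all randomised infants, while the calculation uses treated infants. Whether treated infants are balanced within site decides the sign of the change when sites do not differ.
- **Estimate.** The protocol's general statistical considerations already name the type of estimate, proportions or mean differences with 95% intervals. Only the interval method is left open.
- **Timing.** The protocol's consent section refers to recruitment closure, and SAP version 2 has already changed the primary endpoint. Changing the primary test as well is debatable; adding a stratified analysis is not.

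A reader might infer that ignoring the stratification factor inflates the type I error. It does not: the error goes the conservative way. A reader might also infer that the SAP has abolished the protocol's route for site into the secondary model. That goes too far, because the SAP's covariate list is introduced by *including*, and SAP 5.2 commits to planned analyses in the research plan as well as the SAP. The route is arguably still live, but it is conditional and never reaches the primary test.

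**Conclusion.** The point holds as an optional improvement. Site is used to randomise and then appears in none of the three Fisher tests and in no named covariate. Fisher's test is valid, with size at most 3.95% and power 79.6% at 60 and 40 infants.

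For the exact stratified test, the change in power runs from a loss of up to about 1.8 points (no site differences, treated infants not balanced within site) to a gain of about 3 to 7 points at a logit SD of 1.0 to 1.5. These figures rest on assumed site sizes, normal site effects and analysis of treated infants only. The uncorrected asymptotic version did not lose to Fisher in simulation, but its size is only approximately 5%. The direction and size of the gain in this trial cannot be established from the documents.

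**What to change.** If the data are neither locked nor unblinded, amend SAP 7.3 and 7.4 to:

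- Name one site-stratified Cochran-Mantel-Haenszel analysis for the 24-hour, 48-hour and 1-hour outcomes. The exact conditional version guarantees size; the uncorrected asymptotic version is acceptable if approximate size is. Do not use the continuity-corrected version.
- Fix a rule for pooling very small sites, decided blind to arm.
- Report a site-stratified estimate with a 95% interval from a named method that matches the test: a conditional common odds ratio with the exact test, or a Mantel-Haenszel risk difference with the asymptotic one. Mixing the exact test with an asymptotic risk-difference interval gave conflicting verdicts in about 3% of simulated trials at 22% versus 50%.
- Keep the pooled Fisher test as a sensitivity analysis.
- In the secondary logistic model, account for site by conditioning on it, not with indicators.

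If the data are already locked or unblinded, or a further change to the primary analysis is judged too costly to credibility, keep Fisher as primary and report the stratified analysis as a labelled supportive analysis.

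The cost is a SAP amendment and the small possible power loss above. Pooling the two smallest sites trims that loss from 1.7 to about 1.4 points, at a cost of about 0.5 to 0.6 points at SD 1.5.

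### Fisher's exact test is valid and meets the stated 80% power, but Boschloo's exact test would add 3.7 points at the design point with alpha still at or below 5%

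*SAP*

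**What the plan says.** SAP 7.3 (Primary Hypothesis) specifies that Fisher's "exact test will be used to test the 24 hours seizure termination rate between the two treatment groups". The 48-hour outcome (7.3, Key Secondary Hypothesis) and the 1-hour outcome (7.4, Hypothesis 1) are to be handled in a similar way. SAP 6.2 sets the level: tests for the "primary outcome will be conducted at a two-sided alpha level of 0.05". SAP 5.1 plans no interim efficacy look, so the whole 5% is available at the final test.

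The power statement in SAP 3.4, repeated in the protocol under Power Analysis for Aim 1, names a different test: "Power calculations were based on a 2-sided chi-square test for detecting a difference between two proportions". Its inputs are "With a sample size of 60 LEV subjects and 40 PB subject", "assuming a seizure cessation rate of 50% in the control arm", and the claim "we have 80% power to detect a seizure cessation rate as low as 22" per cent. The stated hypothesis runs the other way: "Treatment with LEV improves the rate of seizure termination at 24 hours in neonates compared with standard PB treatment".

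Neither document gives the actual size or power of Fisher's test, or mentions an unconditional exact test. SAP 6.2 promises 95% confidence intervals for all results, but 7.3 names no interval method.

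**The concern.** Fisher's test conditions on the total number of responders. In a table this small only a few outcomes are possible for each total, so the test usually stops short of the nominal 5%. An unconditional exact test can use most of the remainder while still holding 5% for every common response rate. Treated infants are scarce here: the protocol (section 10) expects about three monitored for each one treated. Power that needs no further infants is therefore worth having on the primary question. The choice also carries over to the 48-hour and 1-hour outcomes.

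**Working it through.** **Inputs.** LEV n = 60, PB n = 40, PB rate 50%, LEV rate 22% (SAP 3.4); two-sided alpha 0.05 (SAP 6.2); Fisher's test (SAP 7.3). With PB at 50%, a LEV rate of 78% gives the same power as 22% by symmetry, so the direction of the hypothesis does not matter here.

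**Step 1: the stated 80%.** For the uncorrected pooled chi-square test named in SAP 3.4:

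- pooled rate = (60 × 0.22 + 40 × 0.50)/100 = 0.332
- SE under the null = √[0.332 × 0.668 × (1/60 + 1/40)] = 0.0961
- SE under the alternative = √[0.22 × 0.78/60 + 0.50 × 0.50/40] = 0.0954
- power = Φ[(0.28 − 1.96 × 0.0961)/0.0954] = Φ(0.960) = 83.1%

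Exact enumeration of that test gives 83.4%. Enumeration of Fisher's test gives 79.6%. The stated 80% therefore matches the planned test, not the test named in SAP 3.4. Fisher reaches exactly 80% at a LEV rate of 21.9%, the chi-square test at 23.0%.

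**Step 2: size of Fisher's test.** There are 61 × 41 = 2,501 possible tables. For a common rate p,

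size(p) = Σ Bin(x; 60, p) × Bin(y; 40, p) over the tables (x, y) that the test rejects.

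On a grid of 1,999 values of p the maximum is 3.95%, at p = 50%. For p from 20% to 80% the size lies between 3.7% and 3.95%; at the pooled design rate of 33.2% it is 3.85%. The uncorrected chi-square test reaches 5.5%, so it is not a safe replacement.

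**Step 3: Boschloo's test.** Order the tables by two-sided Fisher p-value and enlarge the rejection region as long as its maximum size stays at or below 5%. The Fisher p-value cut-off becomes 0.0623. The maximum size is 4.98%. The region holds all 1,696 tables that Fisher rejects plus 32 others, 1,728 in all. An example of an added table is 45/60 (75%) against 22/40 (55%), where the Fisher p-value is 0.0508. Power at 50% against 22% is 83.3%, and 83.3 − 79.6 = 3.7 points.

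**Step 4: how far the gain depends on the assumptions.**

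| Arms (LEV/PB) | PB rate | LEV rate | Fisher | Boschloo | Gain (points) |
|---|---|---|---|---|---|
| 60/40 | 50% | 22% or 78% | 79.6% | 83.3% | 3.7 |
| 60/40 | 50% | 65% | 27.1% | 30.8% | 3.7 |
| 60/40 | 50% | 70% | 46.3% | 52.3% | 6.0 |
| 60/40 | 45% | 73% | 76.5% | 80.9% | 4.4 |
| 60/40 | 30% | 58% | 77.4% | 77.7% | 0.2 |
| 59/41 | 50% | 22% | 81.8% | 83.4% | 1.6 |
| 61/39 | 50% | 22% | 79.3% | 83.3% | 4.0 |
| 57/38 | 50% | 22% | 79.0% | 80.4% | 1.4 |
| 60/36 | 50% | 22% | 78.1% | 78.6% | 0.5 |
| 63/42 | 50% | 22% | 81.3% | 84.7% | 3.4 |

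Gains are taken before rounding.

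**Step 5: which unconditional test.** At 60/40 and 50% against 22%, power is 83.3% for Boschloo with the two-sided Fisher p-value; 82.6% for Boschloo built from two one-sided 2.5% tests; 82.6% for the pooled-z unconditional test; 80.9% for the unpooled-z version; and 79.6%, no gain, for pooled-z built from two one-sided tests.

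**The case against.** The strongest reply is that nothing is broken. Fisher's test is pre-specified in both documents, controls alpha and delivers the stated power. That stands. A reader who sees power computed for a chi-square test and analysis by a more conservative one might infer that the trial is underpowered against its own statement. The documents do not support this: the planned test gives 79.6%, and it is the chi-square test that would have given more.

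A reader might also take the gain to be nearly four points in general, from any unconditional test. It is not. Steps 4 and 5 show that it moves with the rates, the arm sizes and the two-sided definition. Nor are the arm sizes secured. Infants may be randomised during EEG set-up, before seizures are confirmed (protocol section 10, Group C), and the intention-to-treat set is all those randomised (SAP 6.1), so the analysed table need not be 60/40. The 3.7 points illustrate the design point. What does hold for any arm sizes is that Boschloo, ordered by the Fisher p-value, contains Fisher's region and so cannot lose power.

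Third, the change might be thought free. It costs no alpha and no infants, but the SAP is already in its second version because the primary endpoint moved from 48 to 24 hours (SAP 1 and 3.6). A further change to the primary analysis, towards a test that rejects more often, must demonstrably precede unblinding. That stands as a real cost.

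Finally, this is a preliminary phase II trial that reports estimates with intervals, and the choice of test does not alter the estimated difference. Randomisation is stratified by site (SAP 3.1), while the Boschloo calculation assumes two independent binomials with a common rate. Both points limit the importance of the change. The second does not favour Fisher, which as planned also ignores site.

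**Conclusion.** The point holds as a cheap improvement. At 60/40 Fisher's test uses at most 3.95% of the 5% available. Boschloo's test, with the two-sided Fisher p-value as the statistic, uses at most 4.98% and raises power from 79.6% to 83.3% at 50% against 22% or 78%. In the other cases tabulated the gain is 0.2 to 6.0 points, and it is never negative. For scale, Fisher's test with 105 infants (63/42) reaches 81.3% at the design rates, less than Boschloo's test with 100.

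These figures assume independent binomial outcomes, a common rate under the null, no allowance for site, and the arm sizes shown. They do not show that the planned analysis is invalid or short of its stated power. At 50% against 65% power is low with either test (27.1% and 30.8%), so the change does not make the trial adequate for moderate differences.

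**What to change.** Before unblinding, amend the SAP as follows.

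- **7.3 and 7.4:** use Boschloo's unconditional exact test, two-sided, with the two-sided Fisher p-value as the statistic, for the 24-hour, 48-hour and 1-hour comparisons. State the definition in full and check that the software uses it, since the version built from two one-sided tests gives 82.6% rather than 83.3%.
- **Interval:** name one unconditional exact 95% confidence interval for the difference in proportions, and say how a borderline disagreement between interval and p-value will be reported.
- **Sensitivity:** report Fisher's test alongside.
- **3.4:** give the power of the test actually planned: 79.6% if Fisher is kept, 83.3% if Boschloo is adopted, both at 60/40 and 50% against 22%.

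A mid-p test is not an equivalent substitute, because it does not guarantee a size of at most 5%.

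The cost is a few SAP sentences and an R routine. The drawbacks are a test that readers know less well and a second change to the primary analysis after the endpoint change, which should be dated and justified by these design-stage figures. If the change cannot be made before unblinding, keep Fisher as primary and correct only the power text.
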